QTcF	
Preclinical studies determined that TQ has a low potential for QTcF prolongation.
 
Chloroquine does have a propensity to cause QTcF prolongation. A previous TQ drug-drug interaction study concluded that whilst there was no trend over time for increased QTcF intervals in those treated with TQ alone those treated with CQ did experience QTcF prolongation. In those treated with a combination of CQ/TQ there did not appear to be a trend over time for increased QTcF intervals in the CQ/TQ arm beyond those observed on CQ alone. In addition, a TQ thorough QT study did not show elongation of the QTcF at clinical doses.
	
Conduct ECG monitoring in this study and all phase III studies.

Potential Risk of Clinical Significance	Data/Rationale for Risk	Mitigation
Liver Transaminase Elevations	
Preclinical repeat dose toxicology studies observed liver changes that were fully or partially reversible.
 
During a TQ thorough QT study two subjects receiving 1200 mg TQ experienced transient elevations in liver transaminases. It was concluded that high doses of TQ appeared to be associated with transient increases in transaminases.
	Conduct liver function testing in this study and all phase III studies.
Renal Function	
Transient increases in serum creatinine have been observed in clinical studies in adults. A renal safety study was conducted and concluded that TQ, when given as 200 mg x 3 days loading dose followed by weekly 200 mg dosing for 6 months was non-inferior to placebo when comparing mean change from baseline glomerular filtration rate.
 
In TAF112582 study part 1 outliers were characterized by isolated transient rises in creatinine with rapid recovery and no consistent time to onset at a particular dose for the outliers.
 
An in vitro study conducted to better understand and investigate the possible mechanisms involved showed that tafenoquine is an inhibitor of three renal transporters (OCT2, MATE1 and
	
Conduct renal function testing in this study and in all phase III studies.
 
Contra-indicate the use of phenformin, buformin, dofetilide, procainamide and pilsicainide.
 
Exclude subjects taking metformin if the subject has a serum creatinine above the upper limit of normal.

Potential Risk of Clinical Significance	Data/Rationale for Risk	Mitigation

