3.3.1. Dose Rationale

Tafenoquine has demonstrated preliminary efficacy following 1-3 days of dosing, which is further supported by a prolonged half-life of 15-19 days. This shorter course of therapy should significantly improve compliance and thus effectiveness of relapse prevention.

Two separate exploratory clinical studies have demonstrated TQ's utility for the treatment and radical cure of *P. vivax* malaria: Study SB-252263/047 [GlaxoSmithKline Document Number [RM2007/00309/00](#)] was conducted in two parts, and tafenoquine was administered following chloroquine treatment of blood schizonts. Tafenoquine was found to be highly efficacious across the entire 500 mg to 3000 mg dose range. In study SB-252263/058 [GlaxoSmithKline Document Number [UM2004/00017/00](#)], a total dose of 1200 mg tafenoquine was administered over 3 days. Tafenoquine resulted in 100% relapse prevention, however, the tafenoquine monotherapy regimen exhibited slow parasite and fever clearance times relative to the CQ+PQ control. In conclusion, TQ's long half-life supported a 1 to 3 day treatment regimen when co-administered with a second blood schizonticidal drug, such as CQ.

A two-part drug-drug interaction study [GlaxoSmithKline Document Number [WD2009/01503/00](#); Study TAF106491] has also been conducted to investigate the interaction between TQ and CQ in healthy volunteers. Part 1 was a three arm, open label pilot study to evaluate the safety and pharmacokinetics of a low dose CQ co-administered with TQ. Part 2 was a double-blind study to assess the drug-drug interaction, safety (including ECG effects), tolerability and pharmacokinetic parameters of CQ co-administered with TQ. Based on the PK results from the pivotal Part 2 portion of this study, there appears to be a short term significant effect on TQ PK (Day 2 Cmax and AUC(0-24)) when co-administered with CQ with no significant effect on the full PK profile (AUC(0-∞) and t1/2). TQ had no significant effect on the PK of CQ and desethylchloroquine. Taken together, these results suggest that there is no clinically significant pharmacokinetic interaction with concomitant administration of TQ and CQ.

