4.2.2. Exclusion Criteria

Deviations from exclusion criteria are not allowed because they can potentially jeopardize the scientific integrity of the study, regulatory acceptability or subject safety. Therefore, adherence to the criteria as specified in the protocol is essential.

Subjects meeting any of the following criteria must not be enrolled in the study:

Safety

1. The subject has a mixed malaria infection (identified by a malarial smear or rapid diagnostic test).
2. The subject has severe *P. vivax* malaria as defined by WHO criteria.
3. The subject has a history of allergy to chloroquine, mefloquine, tafenoquine, primaquine, or to any other 4- or 8-aminoquinoline.

Hepatic Disease

4. The subject has a liver ALT >2 x ULN.

Concurrent Disease

5. The subject has severe vomiting (no food or inability to take food during the previous 8 hours).
6. The subject has a clinically significant concurrent illness (e.g., pneumonia, septicemia), pre-existing condition (e.g., renal disease, malignancy), condition that

may affect absorption of study medication (e.g., vomiting, severe diarrhea), or clinical signs and symptoms of severe cardiovascular disease (e.g., uncontrolled congestive heart failure, severe coronary artery disease).

7. The subject has a history of porphyria, psoriasis, or epilepsy.
8. The subject has a history of significant ocular disease (e.g. surgery to the globe, glaucoma, diabetic retinopathy) or has evidence of corneal or retinal abnormalities identified in the clinical screening ophthalmologic examination.

Concurrent Medication

9. The subject has taken anti-malarials (e.g., artemisinin-based combination therapies, mefloquine, primaquine, or any other 4- or 8-aminoquinoline) within 30 days prior to study entry.
10. The subject has taken or will likely require during the study the use of medications from the following classes:

- Histamine-2 blockers and antacids
- Drugs with hemolytic potential
- Drugs known to prolong the QTcF interval
- The biguanides phenformin and buformin (but excluding metformin)
- Drugs that are substrates of the renal transporters OCT2, MATE1 and MATE-2K and have a narrow therapeutic index (for example, the anti-arrhythmic agents dofetilide, procainamide and pilsicainide)

Other

11. The subject has received treatment with any investigational drug within 30 days of study entry, or within 5 half-lives, whichever is longer.

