5.6.2. Prohibited Medications and Non-Drug Therapies

The following drugs are prohibited for use from 30 days prior to entry in the study through Day 180:

- Anti-malarials and other medicines with known anti-malarial activity.
- Drugs with hemolytic potential.
- Drugs known to prolong QTcF
- Drugs known to interact with primaquine or chloroquine.

Results from an *in vitro* renal transporters study showed that TQ inhibits the renal transporters MATE1, MATE2-K AND OCT2. Inhibition of these transporters may explain mild, transient, asymptomatic increases of creatinine observed in previous clinical studies and may lead to increased exposure to medications excreted via these transporters. The following drugs are prohibited for a period of 21 days immediately following the blinded dose of tafenoquine.

- The following anti-diabetic drugs of the biguanide class:
 - Phenformin
 - Buformin
- The following anti-arrhythmic drugs:
 - Dofetilide
 - Procainamide
 - Pilsicainide

Metformin, another biguanide anti-diabetic, may continue to be taken provided the subject has serum creatinine below the upper limit of normal and has no concomitant medical condition that increases the risk of lactic acidosis.

The use of herbal remedies during the course of the study is to be avoided. However, if taken this should be recorded in the eCRF under concomitant medication.

See [Appendix 5](#) in Section 11.5 for a non-exhaustive list of prohibited medicines for guidance.

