11.5. Appendix 5: Prohibited Medications for Study Entry

Acetylsalicylic acid. (Paracetamol is the recommended antipyretic agent due to FDA requirement to record times antipyretics are given).

Antimalarials:

- 4-aminoquinolines (amodiaquine, chloroquine)
- 8 aminoquinolines (primaquine, pamaquine)
- Artemisinin derivatives
- Aryl-aminoalcohol (halofantrine, lumefantrine)
- Atovaquone
- Tetracycline e.g. doxycycline
- Quinine, Quinidine, Quinacrine, mefloquine
- Proguanil

Drugs with antimalarial activity:

This list serves to provides examples of more commonly used drugs with antimalarial activity, but is not exhaustive.

- Albendazole
- Allopurinol
- Clindamycin
- Diamidines (e.g., Pentamidine)
- Fluroquinolones e.g. ciprofloxacin, Nalidixic acid sparfloxacin
- Glibenclamide
- Indinavir, Saquinavir and Ritonavir
- Isoniazid
- Probenecid
- Rifampicin
- Sulfadiazine, Sulfadoxine or Sulfalene/pyrimethamine, Sulfamethoxazole/trimethoprim, Sulfasalazine (and other sulfonamides)
- Sulfacetamide

Drugs known to cause QTcF prolongation:

- Arsenic trioxide
- Bepridil
- Chlorpromazine
- Cisapride
- Disopyramide
- Dofetilide
- Domperidol
- Droperidol
- Haloperidol
- Ibutilide
- Isotalol
- Ketoconazole (oral or IV, topical preparations are allowed)
- Levomethadyl
- Lidoflazine
- Macrolides (Azithromycin, Erythromycin, Clarithromycin, Roxithromycin)
- Mesoridazine
- Methadone
- Pentamidine
- Pimozide
- Probucol
- Procainamide hydrochloride
- Terfenadine
- Thioridazine
- Sulfapyridine

Drugs Contraindicated in G6PD deficiency:

- Melarsoprol
- Menadiol
- Methyl dopa-
- Methylthioninium chloride (i.e., Methylene Blue)

- Nalidixic acid
- Niridazole
- Nitrofurantoin

Drugs excreted via the renal transporters MATE1, MATE2-K AND OCT2:

The following drugs excreted via the renal transporters MATE1, MATE2-K AND OCT2 are prohibited for a period of 21 days immediately following the blinded dose of tafenoquine.

- Phenformin
- Buformin
- Dofetilide
- Procainamide
- Pilsicainide

Metformin is also excreted via MATE1, MATE2-K AND OCT2, but may continue to be taken, provided the subject has a serum creatinine below the upper limit of normal and has no concomitant medical conditions that increase the risk of lactic acidosis.

Others-miscellaneous:

- Phenazopyridine
- Phenylhydrazine
- Chloramphenicol

CQ interactions (source eMC):

- Amiodarone

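### Protocol Amendment 5 gives different rules for a metformin user with raised creatinine, and lists dofetilide and procainamide under two bars with different end dates

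*Supplement*

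**What the plan says.** All references are to Protocol Amendment 5.

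- **Section 1.3.1, Table 1, Renal Function, mitigation column.** On metformin: "Exclude subjects taking metformin if the subject has a serum creatinine above the upper limit of normal". On the other transporter drugs: "Contra-indicate the use of phenformin, buformin, dofetilide, procainamide and pilsicainide", with no time limit.
- **Section 4.2.2, criterion 10.** A subject who has taken, or is likely to need during the study, certain classes is excluded. One class is "The biguanides phenformin and buformin (but excluding metformin"). Another is narrow-therapeutic-index substrates of the renal transporters, with dofetilide, procainamide and pilsicainide as examples. Creatinine is not mentioned.
- **Section 5.6.2.** A general list, which includes QTcF-prolonging drugs, opens with "The following drugs are prohibited for use from 30 days prior to entry in the study through Day 180". The list of five transporter drugs opens with "The following drugs are prohibited for a period of 21 days immediately following the blinded dose of tafenoquine". Metformin "may continue to be taken provided the subject has serum creatinine below the upper limit of normal", and only if no concomitant condition raises the risk of lactic acidosis.
- **Section 11.5, Appendix 5.** This repeats the 21-day transporter list and the metformin condition. Its separate QTcF list also contains dofetilide and "Procainamide hydrochloride".

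**The concern.** Table 1 is where the protocol sets out how it will contain each known risk, and Section 4.2.2 is the list a site works through before randomising. The metformin mitigation is in the first and not in the second. A site reading criterion 10 finds metformin expressly set apart from the barred biguanides. A site reading Table 1 finds an instruction to exclude. A site reading Section 5.6.2 or Appendix 5 finds a condition on the drug and no statement about the subject.

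The safeguard was added because tafenoquine inhibits renal transporters and may raise exposure to drugs excreted through them. Two sites could handle the same patient differently, each with a section to point to. The protocol allows neither waivers (Section 3.2) nor deviations from the exclusion criteria, so the list has to say what is meant.

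There is also a reporting consequence. Section 4.1 of the latest analysis plan bases its separate summary of eligibility deviations on the inclusion/exclusion page of the eCRF. If that page mirrors Section 4.2.2 (an assumption, since the page is not shown), enrolling a patient whom Table 1 would exclude would not appear in that summary.

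The overlapping drug windows raise a smaller question of the same kind: which end date applies to a drug that is on both lists.

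**Working it through.** No sample size, error rate or event count is involved. The check sets the passages side by side and does one day-count.

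**Step 1. Metformin users, by creatinine and section**

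| Patient on metformin | Table 1 | Criterion 10 | 5.6.2 and Appendix 5 |
|---|---|---|---|
| Creatinine above ULN | Exclude the subject | Not excluded | Metformin may not continue; silent on the subject |
| Creatinine exactly at ULN | Not excluded (rule says *above*) | Not excluded | Metformin may not continue (rule says *below*) |
| Below ULN, lactic acidosis risk condition | Not excluded | Not excluded | Metformin may not continue |
| Below ULN, no such condition | Not excluded | Not excluded | Metformin may continue |

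The sections agree only in the last row. In the first row the open question is whether the subject is excluded or enters without metformin. In the second, the two creatinine rules differ at the boundary. In the third, a condition in Section 5.6.2 and Appendix 5 has no counterpart in Table 1 or criterion 10.

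**Step 2. Does another exclusion criterion close the gap?** Criterion 6 names renal disease as an example of a pre-existing condition but gives no creatinine threshold. Criterion 2 excludes severe malaria, and Appendix 4 counts creatinine above 265 µmol/L as acute renal failure within that definition. That is a fixed value, not one tied to ULN, and it does not depend on metformin. Neither criterion reproduces the Table 1 rule, though each may catch some of these patients.

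**Step 3. On-study bars for the five named transporter drugs**

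| Drug | 21 days after the blinded dose | 30 days before entry through Day 180 (QTcF list) |
|---|---|---|
| Dofetilide | Yes | Yes |
| Procainamide | Yes | Yes |
| Phenformin | Yes | Not listed |
| Buformin | Yes | Not listed |
| Pilsicainide | Yes | Not listed |

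The overlap concerns 2 of the 5 drugs.

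**Step 4. Distance between the two end dates.** Blinded medication starts on Day 1 or Day 2 (Section 5.1.7).

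- Dose on Day 1: 1 + 21 = Day 22; 180 − 22 = 158 days.
- Dose on Day 2: 2 + 21 = Day 23; 180 − 23 = 157 days.

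For these two drugs the end dates are about 157 to 158 days apart. The 21-day bar also has no pre-entry period, while the other starts 30 days before entry.

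**The case against.** The best defence is that the creatinine safeguard is in the operational text. Section 5.6.2 and Appendix 5 both make continued metformin conditional on creatinine below ULN, and Appendix 5 is headed as a list for study entry. The metformin exemption in criterion 10 says only that this bullet does not cover metformin; it does not declare a user with raised creatinine eligible. Every passage that mentions creatinine agrees that a patient above ULN should not be taking metformin in the study. This stands, and it rules out saying that the safeguard is absent or that sites have nothing to apply. It does not settle whether the subject is excluded or the drug is stopped, nor the case exactly at ULN.

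On the windows, criterion 10 is an entry screen and may properly be broader than an on-study ban, so its open-ended look-back is no contradiction. The 21-day and Day 180 bars have different rationales and can be read as cumulative, in which case satisfying one does not lift the other. A reader might infer that the 21-day sentence lets a site restart dofetilide or procainamide after it ends. No such permission is written. What remains is that the protocol does not say the bars are cumulative, and the shorter one is the one that names the drugs in the section itself.

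A reader might also infer from the stated half-life ("further supported by a prolonged half-life of 15-19 days") that 21 days is too short. The documents do not support that. They give no concentration at which transporter inhibition becomes relevant, and the length of the bar is a clinical judgement.

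**Conclusion.** The metformin passages contradict each other on one point that matters at entry: Table 1 excludes the subject, criterion 10 does not, and Section 5.6.2 and Appendix 5 restrict only the drug. The boundary at ULN is also inconsistent. The binding exclusion list therefore does not carry the mitigation stated in the protocol's own risk table.

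The window point is secondary. It is an ambiguity for dofetilide and procainamide, not a conflict across all five drugs, and it disappears if the sponsor states that the bars are cumulative.

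The practical size is small. The documents do not say how many patients take these drugs; in this population it is assumed to be few. Nothing here touches the primary endpoint, the sample size or the primary analysis. The case for acting is that this is a safety rule and the correction costs little.

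**What to change.** Reconcile Table 1, criterion 10 of Section 4.2.2, Section 5.6.2 and Appendix 5 as follows.

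1. State one rule for a patient on metformin with raised creatinine. It should say whether the subject is excluded or the drug is stopped, what happens at exactly ULN, and whether the lactic acidosis condition applies at entry. Put the rule in the numbered eligibility list and make the other three places match it.
2. For drugs that appear on both the transporter list and the QTcF list, state which window governs, or that both apply.

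The sponsor's clinicians choose the rule and the end date; this point recommends neither. The cost is wording in an amendment and a matching check of the eCRF eligibility page. No new test is needed, because serum creatinine is already part of the screening chemistry (Section 6.1). Depending on the rule chosen, there may be a very small number of extra screen failures.

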1.3.2. Benefit Assessment

In the absence of radical cure treatment, a percentage of patients with *P. vivax* malaria will relapse due to the liver being infected with hypnozoites (the dormant form of the parasite). *P. vivax* malaria is most prevalent primarily in Asia, Asia-Pacific and Latin American countries and frequency of relapse rates may impact product use. Relapse rates vary with strain and are difficult to measure due to confounding by re-infection. The WHO have generalized relapse rates in the following countries as: India (15-20%), Indonesia (30%) and South East Asia (50-60%). *P. vivax* can cause a debilitating fever and as it preferentially invades reticulocytes, can also lead to the development of anemia. Repeated relapses are similarly debilitating and may result in further episodes of fever, weight loss, malnutrition and high output heart failure, especially in children. Consequences are loss of work or school days (e.g. 5.4 days school absenteeism per episode) and hospitalization (especially children) due to vomiting, dehydration and anemia (resulting in transfusion).

Due to its long half life, tafenoquine can be administered as a single oral dose and is therefore a more convenient treatment regimen with the potential to improve patient compliance. Improved compliance could also lead to improved clinical outcomes for patients with *P. vivax* malaria by further reducing relapse rates.

1.3.3. Overall Benefit:Risk Conclusion

Tafenoquine is being developed with the aim of a benefit:risk profile which is as least as good as the current gold standard therapy PQ. Our intent is to evaluate whether improved compliance could also lead to improved clinical outcomes for patients. Tafenoquine should have no clinically significant side effects that will restrict its use as a first line agent in treatment of *P. vivax* malaria when used in combination with a G6PD test and recommended therapies to treat the blood stages of infection. With specific regard to this study, the overall benefit:risk is favorable to all subjects, given that all are receiving active treatment.

2. OBJECTIVES & ENDPOINTS

Objectives	Endpoints
Primary	

To investigate the occurrence of clinically relevant hemolysis in adult subjects with P. vivax. The incidence of hemolysis in the subgroup of female patients with moderate (40-70%) G6PD activity is of particular interest.
	
 • Occurrence of clinically relevant hemolysis in all subjects; defined as, a decrease in hemoglobin of $\geq 30\%$ or >3 g/dL from baseline; or, an overall drop in hemoglobin below 6.0 g/dL. • Occurrence of clinically relevant hemolysis in female subjects with moderate (40-70%) G6PD deficiency; defined as, a decrease in hemoglobin of $\geq 30\%$ or >3 g/dL from baseline; or, an overall drop in hemoglobin below 6.0 g/dL.
Secondary	

To compare the clinical and parasitological efficacy, safety and tolerability of tafenoquine to primaquine as a radical cure for adult subjects with P. vivax malaria when co-administered with chloroquine.
	
 • Relapse-free efficacy six months post-dosing • Relapse-free efficacy four months post-dosing • Time to relapse • Parasite clearance time • Fever clearance time • Gametocyte clearance time • Recrudescence, defined as any P. vivax parasitemia occurring on or before Day 32 (i.e., blood stage treatment failure). • Incidence of genetically homologous and genetically heterologous P. vivax infections (determined by PCR) • Safety evaluation of data from clinical laboratory tests, urinalysis, spontaneous/elicited adverse event reporting, ECGs and vital signs in all subjects who received at least one dose of study medication. • Incidence of P. falciparum malaria

[figure not shown]
Objectives	Endpoints
To characterize the socioeconomic impact of P. vivax relapse.	
 Characterization of healthcare resource use and socio-economic impact of P. vivax relapses and adverse events caused by treatment to prevent P. vivax relapses, especially hemolytic anemia.
To evaluate the pharmacokinetics of tafenoquine in the treatment of adult subjects with P. vivax malaria.	
 Population PK parameters for tafenoquine including but not limited to oral clearance (CL/F) and volume of distribution (V/F)
To characterize the pharmacokinetic/pharmacodynamic relationship in this study population.	
 PK and selected PD endpoints (e.g., relapse-free efficacy, change in methemoglobin) if appropriate

With regard to the secondary efficacy endpoints, it should be noted that it is not possible to determine if a subject's recurrence of malaria is a relapse or a re-infection. For the purposes of this protocol, the term "relapse" will be used to describe any recurrence of malaria that occurs after Day 32 of the study. "Recrudescence" applies to the term relating to recurrence for Days 1 to 32 of the study where, although a genetically homologous parasite is highly suggestive of recrudescence and thus blood stage treatment failure, it is not absolute as re-infection is technically possible; the probability of which is related to the overall background incidence of the homologous parasite in the mosquito population.

